8.2. Safety Assessments

Participants must be evaluated by a physician or an appropriately trained health care professional at every visit and the evaluation must be documented. The procedures discussed below will be completed at the designated visits. Safety assessments should not be administered to the participant unless the participant is accompanied by his or her consented caregiver.

The safety parameters will comprise physical examination, AEs, clinical laboratory parameters (clinical chemistry, CBC, urinalysis), vital signs, postural vital signs, height, weight, and ECG.

Evidence of severe diarrhea, especially when accompanied by dehydration, volume depletion and/or significant electrolyte or ECG abnormalities will be actively monitored throughout the study.

All AEs will be monitored until symptom resolution or until the condition stabilizes. A DSMB will oversee AEs and safety of the overall study.

Planned timepoints for all safety assessments are provided in the SoAs (Section 1.4 FC participants and Section 1.5 IBS-C participants).

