2.2 Study Design Overview

LIN-MD-66 is a long-term study with 24 weeks (FC participants) or 52 weeks (IBS-C participants) of linaclotide exposure that will enroll pediatric participants (6-17 years of age) with FC or IBS-C who completed study intervention in the Phase 2 study LIN-MD-62 or LIN-MD-63, or Phase 3 study LIN-MD-64, based on individual study criteria. For FC participants enrolling from studies LIN-MD-62 and LIN-MD-64, and IBS-C participants enrolling from study LIN-MD-63, linaclotide treatment will be open-label. For IBS-C participants enrolling from study LIN-MD-64, linaclotide

treatment will be either blinded or open-label. Linaclotide treatment will be blinded if participants choose to remain on the same blinded linaclotide dose they were receiving in the lead-in LIN-MD-64 study and will be open-label if participants choose to receive open-label linaclotide therapy.

- Phase 2 completers are defined as pediatric participants who completed 4-week double-blind study intervention and end of treatment (EOT) Visit (Visit 5) in the Phase 2 studies AND
 - Completed the end of study (EOS) (Visit 6) in Study LIN-MD-62 or
 - Completed the EOS (Visit 6) in Study LIN-MD-63. However, this EOS Visit in LIN-MD-63 is not required for participants who enroll into LIN-MD-66 prior to that visit.
- Phase 3 completers are pediatric participants who completed 12-week double-blind study intervention in Study LIN-MD-64. Participants must have completed the EOT visit (Visit 7) and the EOS visit (Visit 8). However, this EOS visit in LIN-MD-64 is not required for participants who enroll into LIN-MD-66 prior to that visit.

[figure not shown]
The present study will include a screening period and a 24-week (FC participants) or 52-week (IBS-C participants) study intervention period. For participants who enroll in LIN-MD-66 on the same day as their EOT Visit or EOS Visit in LIN-MD-64, the EOT Visit or EOS Visit, respectively, may be combined with the Screening (Visit 1) and Day 1 Visit (Visit 2) in LIN-MD-66. For participants who enroll within \leq 28 days from last study intervention in Study LIN-MD-64 (Visit 7), the LIN-MD-66 Screening Visit (Visit 1) and Day 1 Visit (Visit 2) procedures may be combined, with the exception of participants who are positive for fecal impaction assessment at the Screening Visit (Visit 1).

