9.2.1 Treatment-Emergent Adverse Events

An AE will be considered a treatment emergent adverse event (TEAE) if:

- The AE began on or after the date of the first dose of study intervention in LIN-MD-66; or
- The AE was present before the date of the first dose of study intervention in LIN-MD-66 but increased in severity or became serious on or after the date of the first dose of study intervention in LIN-MD-66.

However, an AE that occurs more than 30 days after the last dose of study intervention in LIN-MD-66 will not be counted as a TEAE.

An AE will be considered a treatment emergent serious adverse event (TESAE) if it is a TEAE that additionally meets any serious adverse event (SAE) criterion.

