9.2.7 Diarrhea Treatment Emergent Adverse Events

The TEAE summary by SOC and PT will be provided for those subjects who had a TEAE of diarrhea, regardless of whether these TEAEs occurred concurrently.

The following information will be summarized for the subjects who had a diarrhea TEAE. Each diarrhea TEAE for each subject shall be counted as a separate event for the summaries described in the first 2 bullets below.

- The number and percentage of subjects with a 1 or more diarrhea TEAE events, with 2 or more diarrhea TEAE events, and with 3 or more diarrhea TEAE events.
- The number and percentage of diarrhea TEAEs with an end date, and ongoing at the end of the study.
- Descriptive statistics for the time to onset of the first diarrhea TEAE. The number and the percentage of subjects with diarrhea TEAE will be summarized by time to onset of first occurrence using the following time intervals: Day 1, Day 2, Day 3-7, Week 2 to Week 11 (for each week), and Week 12 and later.
- The longest duration of diarrhea TEAEs within a subject will be summarized. For those subjects with at least one diarrhea TEAE ongoing at the end of the study, the subject will be counted in the 'Ongoing' category. The number and the percentage of subjects classified according to their longest diarrhea duration or ongoing will be summarized by the following duration intervals: 1 day, 2 days, 3-7 days, 8-14 days, 15-28 days, >28 days, and ongoing. The descriptive statistics for the duration of the longest duration of diarrhea TEAE with an end date for subjects will be presented.

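### SAP 9.2.7 takes its diarrhea duration statistics from resolved episodes only, so they understate duration, by an unknown amount, whenever episodes are ongoing

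*SAP*

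**What the plan says.** SAP 9.2.7 summarises each subject's longest diarrhea TEAE in two ways.

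- **Categorical table.** The rows are "1 day, 2 days, 3-7 days, 8-14 days, 15-28 days, >28 days, and ongoing". The last row takes precedence: "For those subjects with at least one diarrhea TEAE ongoing at the end of the study, the subject will be counted in the 'Ongoing' category".
- **Continuous statistics.** These are restricted: "The descriptive statistics for the duration of the longest duration of diarrhea TEAE with an end date for subjects will be presented".

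Another bullet of the same section reports, at event level, "The number and percentage of diarrhea TEAEs with an end date, and ongoing at the end of the study". SAP 9.2.3 lists all AEs. No table gives the elapsed time of an ongoing episode, and no method for censored durations is named. The SAP does not say whether a subject with both a resolved and an ongoing episode enters the continuous statistics.

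On follow-up, Protocol 8.2 states: "All AEs will be monitored until symptom resolution or until the condition stabilizes". Protocol 8.3.2 collects AEs until 30 days after the last dose. The schedules of activities show no visit after EOT, and Protocol 8.3.4 provides a follow-up visit only where it is judged necessary.

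**The concern.** An ongoing episode is a right-censored duration: its observed length is a lower bound. At any given onset date, a longer episode is more likely to be unresolved when observation stops, so selecting episodes with an end date favours the shorter ones. The mean and median of the selected set are then too low as descriptions of how long diarrhea lasts.

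The categorical table has a related gap. Because the ongoing row takes precedence, a subject with a resolved 60-day episode and a new ongoing one, or with 100 days of ongoing diarrhea, is not counted in the >28-day row. That row is a floor but is not labelled as one. Diarrhea ongoing for 2 days and for 100 days looks the same.

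The study's only objective is long-term safety. Diarrhea was the most frequent TEAE in both pediatric Phase 2 studies (Protocol 2.2.2), and Protocol 8.3 asks for particular attention to it. How long it persists is what readers will look for in this table.

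**Working it through.** The documents state no expected diarrhea duration, so there is no figure of the plan's own to reproduce. The check has three parts.

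**1. How few subjects are involved.** Protocol 2.2.2 gives diarrhea in 7.6% of linaclotide-treated participants in the 4-week FC study (36 + 41 + 39 + 16 = 132 treated; 10/132 = 7.6%). Applied to the planned minimum of 120: 0.076 × 120 = 9.1 subjects. Longer exposure may give more. SAP 9.1 then splits results by indication, dose group and age, so one or two ongoing episodes can move a group's mean and maximum.

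**2. A small example (invented data).** Eight resolved episodes of 1, 2, 2, 3, 4, 6, 8 and 12 days sum to 38.

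- Resolved only: mean 38/8 = 4.75, median 3.5, maximum 12.
- Add two ongoing at 60 and 150 days, as lower bounds: mean (38 + 210)/10 = 24.8, median 5.0, maximum 150.
- Add instead two ongoing at 3 and 5 days: mean (38 + 8)/10 = 4.6, median 3.5, maximum 12.

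Under SAP 9.2.7, if these are ten different subjects, both cases give the same continuous statistics and the same ongoing count of 2.

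**3. Range of the bias (simulation, all durations and onsets assumed).** Each subject has one episode with duration D lognormal, so true mean = median × exp(SD²/2). For example, 7 × exp(1.125) = 21.6 days and 10 × exp(1.125) = 30.8 days. The treatment period T is 168 days (FC) or 364 days (IBS-C), from 24 and 52 weeks. An episode with onset at time t has an end date if D ≤ T + F − t, where F is follow-up after the last dose (0 or 30 days). Onset is uniform over T, or early (exponential, mean 14 days). There were 2,000,000 episodes per setting.

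| Group, onset | True median | Log-SD | F | Ongoing | Resolved-only median | Resolved-only vs true mean | Mean understated by |
|---|---|---|---|---|---|---|---|
| FC, uniform | 3 | 1.0 | 30 | 0.1% | 3.0 | 4.9 vs 4.9 | about 1% |
| FC, uniform | 7 | 1.0 | 30 | 0.9% | 6.9 | 10.9 vs 11.5 | 6% |
| FC, uniform | 10 | 1.0 | 30 | 2.0% | 9.8 | 14.8 vs 16.5 | 10% |
| FC, early | 7 | 1.5 | 30 | 1.5% | 6.8 | 16.4 vs 21.6 | 24% |
| FC, uniform | 7 | 1.5 | 0 | 11.1% | 5.8 | 12.2 vs 21.6 | 44% |
| FC, uniform | 10 | 1.5 | 0 | 14.9% | 7.8 | 15.2 vs 30.8 | 51% |
| IBS-C, uniform | 7 | 1.5 | 0 | 5.6% | 6.4 | 15.3 vs 21.6 | 29% |
| IBS-C, uniform | 10 | 1.5 | 0 | 7.7% | 8.8 | 19.8 vs 30.8 | 36% |

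In the FC setting with a 7-day median, log-SD 1.5 and no follow-up, the >28-day row holds about 10% of subjects with diarrhea against a true 17.8%. About 4.5 percentage points of that gap are ongoing episodes already observed beyond 28 days. Where a Kaplan-Meier median with ongoing episodes censored was computed (true medians of 3, 7, 14 and 28 days), it came within about half a day of the true median.

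**The case against.** The strongest reply is that the plan hides nothing. Subjects with ongoing diarrhea stay in the categorical table, ended and ongoing events are counted, every AE is listed, and the continuous statistic is labelled as resting on episodes with an end date. It describes resolved episodes correctly. The study is descriptive: SAP 11.0 rules out inferential testing, and SAP 9.1 summarises safety data as observed. No test or sample size depends on this number. All of that stands. What remains is that a count of exclusions does not show how long the excluded episodes lasted.

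Follow-up to resolution or stabilization should also keep the number of ongoing episodes small. This stands in part. Follow-up may end on stabilization, so stable, persistent diarrhea can stay without an end date, and no visit after EOT is scheduled.

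Three stronger readings are tempting, and the documents do not support them.

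- *That the rule drops the longest episodes.* It drops longer ones preferentially. An episode that began recently may have lasted only a few days. With uniform onset and no follow-up, 23% to 47% of ongoing episodes had an elapsed time at or below the resolved-only median.
- *That the mean will be understated by a quarter to a half.* That needs a long-tailed duration (log-SD 1.5), uniform onset and no follow-up. The mean is also sensitive to an assumed tail, and a Kaplan-Meier median would not report it.
- *That the SAP enters a subject with a short resolved and a long ongoing episode at the short value.* The text allows this reading but does not prescribe it.

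**Conclusion.** The point holds as a modest improvement to a descriptive table. The direction is clear: whenever ongoing episodes exist, resolved-only statistics tend to understate how long diarrhea lasts. The size cannot be fixed from the documents, because they give neither durations nor an expected ongoing share. With assumed lognormal medians of 3 to 10 days, it ranges from essentially none (3-day median, log-SD 1.0, 30 days of follow-up) to a mean understated by about 50% and a median by about 2 days (10 vs 7.8 days; log-SD 1.5, uniform onset, no follow-up, FC). At log-SD 1.0 with 30 days of follow-up and medians up to 7 days, the mean is low by about 6% or less and the median by at most 0.1 day. The gaps in elapsed time and in the >28-day row follow from the wording and need no simulation.

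**What to change.** In SAP 9.2.7:

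1. Keep the resolved-only statistics, label them as such, and print the number of subjects with an ongoing episode beside them.
2. Add a summary of each subject's longest episode with ongoing episodes censored at last contact: Kaplan-Meier median and percentage lasting more than 28 days, where estimable. At minimum, tabulate elapsed days for ongoing episodes, marked as lower bounds.
3. State that a subject with both resolved and ongoing episodes contributes the longest observed duration, marked as censored if that episode is the ongoing one. If the longest observed episode is resolved but a shorter one is still ongoing, a footnote should say that the value could still be exceeded.

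The cost is SAP wording and some programming, using onset, end and last-contact dates; no new assessments are needed. Kaplan-Meier quantiles may not be estimable in small dose-by-age groups, so present them overall by indication and use the elapsed-days table elsewhere. Censoring at last contact treats it as unrelated to remaining duration. That is doubtful where follow-up stopped because the condition had stabilized, which is a further reason to show the elapsed days.

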9.3 Analysis of Laboratory Data

Descriptive statistics for clinical laboratory values (in International System of Units [SI] units) and changes from the baseline values at each assessment time point will be presented by study intervention group for the following clinical laboratory parameters.

Hematology: Platelet count, red blood cell (RBC) count, hemoglobin, hematocrit, RBC indices (mean corpuscular volume, mean corpuscular hemoglobin, and mean corpuscular hemoglobin concentration), white blood cell count with differential (Neutrophil, Lymphocytes, Monocytes, Eosinophils, Basophils), and

Chemistry: Blood urea nitrogen, creatinine, glucose, potassium, sodium, bicarbonate, magnesium, phosphate, total protein, calcium, aspartate aminotransferase (AST), alanine aminotransferase (ALT), alkaline phosphatase, total bilirubin, direct and indirect bilirubin, total cholesterol, chloride, albumin, and

Urinalysis: Specific gravity and pH

Clinical laboratory test values will be considered potentially clinically significant (PCS) if they meet either the lower-limit or higher-limit PCS criteria listed in Table B-1 in [Appendix B](#). The number and percentage of participants who have at least one PCS post-baseline clinical laboratory value will be tabulated. The percentages will be calculated based on the denominator of the number of participants with available non-PCS baseline values and at least one post-baseline value and the numerator of the number of participants with non-PCS baseline value and at least one PCS post-baseline value. A supportive listing of participants with post-baseline PCS values will be provided.

In addition, a tabular display showing all AEs that occurred in participants who had PCS postbaseline clinical laboratory values will be provided.

Shift tables from baseline to the end of Intervention Period for clinical laboratory parameters listed above will be presented by study intervention group for the following categories: low, normal, and high, which are provided by lab vendor.

Potential Hy's Law Cases

Potential Hy's Law criteria within a 24-hour window is defined by a post baseline elevation of ALT or AST $\geq 3 \times \text{ULN}$, along with TBL $\geq 2 \times \text{ULN}$ and a non-elevated ALP $< 2 \times \text{ULN}$, all based on blood draws collected within a 24-hour period.

Participants who meet the potential Hy's Law criteria from the first dose of study intervention to within 30 days after the last dose of study intervention will be summarized. Supportive tabular displays will also be provided.

9.4 Analysis of Vital Signs

Descriptive statistics for vital signs (supine systolic and diastolic blood pressure, supine pulse rate, respiration rate, and temperature, and weight) and their changes from baseline at each assessment timepoint will be presented for each vital sign measurement.

Vital sign values will be considered to be PCS values if they meet both the observed-value criteria and the change-from-baseline-value criteria as defined in Table B-2 in [Appendix B](#). The number and percentage of participants who have PCS postbaseline vital sign values will be tabulated. The percentages will be calculated relative to the number of participants who have available non-PCS baseline values and at least 1 postbaseline assessment. The numerator will be the total number of participants with at least 1 PCS postbaseline value. A supportive listing of participants with PCS postbaseline values will be provided for the Safety Population.

In addition, a tabular display showing all AEs that occurred in participants who had PCS postbaseline vital sign values will be provided.

9.5 Electrocardiogram

Descriptive statistics for ECG parameters (i.e., ventricular heart rate, RR interval, PR interval, QRS interval, QT interval, and QTc) and changes from baseline values at each assessment time point will be presented. The QTc is calculated using both the Bazett and Fridericia corrections.

ECG parameter values are considered PCS if they meet or exceed the higher-limit PCS criteria listed in Table B-3 of the [Appendix B](#). The number and percentage of participants with PCS postbaseline ECG values will be tabulated. The percentages will be calculated relative to the number of participants with available non-PCS baseline values and at least 1 postbaseline assessment. The numerator will be the total number of participants with available non-PCS baseline values and at least 1 PCS postbaseline value. A supportive listing of participants with PCS postbaseline values will be provided for the Safety Population.

In addition, a tabular display showing all AEs that occurred in participants who had postbaseline PCS ECG values will be provided.

A shift table from baseline to the end of Intervention Period in the Investigator's overall interpretation of the ECG will be presented by study intervention group for the following categories: normal; abnormal, not clinically significant; abnormal, clinically significant. A tabular display showing participants with postbaseline clinically significant ECG abnormalities according to the Investigator's overall interpretation will be provided.

10.0 Interim Analyses

Interim analysis(es) to assess long-term safety of linaclotide may be performed after at least 120 participants have completed the study. Data will be locked after performing data cleaning. Results from the interim analysis(es) will be described in an interim clinical study report.

10.1 Data Monitoring Committee

An independent Data Safety Monitoring Board (DSMB) is reviewing safety data at defined intervals throughout the study. DSMB can also request ad hoc review if needed. The DSMB will communicate their recommendations to the sponsor after each meeting but will serve in an advisory capacity only. Further details of the DSMB (composition, policy, and procedures) are specified in a separate DSMB Charter.

11.0 Overall Type-I Error Control

There is no multiplicity adjustment since there is no statistical hypothesis in this study. No inferential testing will be performed.

12.0 Version History

Table 2. SAP Version History Summary

Version	Date	Summary
1.0	08 Nov 2021	Original version
2.0	19 Jul 2022	
Clarified study drug duration summary categories.Added summary for total continuous exposure of linaclotide across lead-in studies and long-term safety study.Modified TEAE definition to include any AE that occurs within 30 days (instead of 1 day) after the last dose of study intervention.Added Exposure-Adjusted Incidence Rate (EAIR) analysis for TEAE overview and TEAE by SOC and PT.Added additional analyses for Diarrhea TEAE.Included age of 18 years old in PCS criteria for clinical laboratory parameters, vital signs, and ECG parameters.

Appendix A. Protocol Deviations

Unique participants reporting significant protocol deviations will be summarized by study intervention group using the safety population, for overall and for each age group (6 to 11 years and 12 to 18 years in FC; 7 to 11 years and 12 to 18 years in IBS-C) separately for FC and IBS-C participants.

A listing of any significant protocol deviations will be provided.

Appendix B. Potentially Clinically Important Criteria for Safety Endpoints

The potentially clinically significant criteria for clinical laboratory parameters, vital signs and ECG parameters are provided in the following sections.

Table B-1. Criteria for Potentially Clinically Significant Laboratory Results

Parameter	SI Unit	Lower Limit	Higher Limit
Chemistry			
Albumin	g/L	< 0.9 × LLN	> 1.1 × ULN
Alanine aminotransferase (ALT)	U/L	—	≥ 3 × ULN
Alkaline phosphatase	U/L	—	≥1.2 x ULN: 6-12 (inclusive), male & female; 13-15 (inclusive), male ≥ 3 × ULN: 13-15 (inclusive), female; 16-18 (inclusive), male & female
Aspartate aminotransferase (AST)	U/L	—	≥ 3 × ULN
Bicarbonate	mmol/L	< 0.9 × LLN	> 1.1 × ULN
Bilirubin, total	μmol/L	—	> 1.5 × ULN
Calcium	mmol/L	< 0.9 × LLN	> 1.1 × ULN
Chloride	mmol/L	< 0.9 × LLN	> 1.1 × ULN
Cholesterol, Total	mmol/L	—	> 1.6 × ULN
Creatinine	μmol/L	—	> 1.3 × ULN
Glucose, random, serum	mmol/L	< 0.8 × LLN	> 1.4 × ULN
Potassium	mmol/L	< 0.9 × LLN	> 1.1 × ULN
Protein, total	g/L	< 0.9 × LLN	> 1.1 × ULN
Sodium	mmol/L	< 0.9 × LLN	> 1.1 × ULN
Magnesium	mmol/L	< 0.9 x LLN	> 1.1 x ULN
Urea Nitrogen (BUN)	mmol/L	—	> 1.2 × ULN
Hematology			
Basophils, absolute cell count	10 ⁹ /L	—	> 3 × ULN
Eosinophils absolute cell count	10 ⁹ /L	—	> 3 × ULN
Lymphocytes absolute cell count	10 ⁹ /L	< 0.7 × LLN	> 1.3 × ULN
Monocytes, absolute cell count	10 ⁹ /L	< 0.5 × LLN	> 2.0 × ULN
Neutrophils, absolute cell count	10 ⁹ /L	< 0.8 × LLN	> 1.5 × ULN

Parameter	SI Unit	Lower Limit	Higher Limit
Hematocrit	Ratio	$< 0.9 \times \text{LLN}$	$> 1.1 \times \text{ULN}$
Hemoglobin	g/L	$< 0.9 \times \text{LLN}$	$> 1.1 \times \text{ULN}$
Platelet count	$10^9/\text{L}$	$< 0.5 \times \text{LLN}$	$> 1.5 \times \text{ULN}$
Red blood cell count	$10^{12}/\text{L}$	$< 0.9 \times \text{LLN}$	$> 1.1 \times \text{ULN}$
White blood cell count	$10^9/\text{L}$	$< 0.7 \times \text{LLN}$	$> 1.5 \times \text{ULN}$
Urinalysis			
pH	—	$< 0.9 \times \text{LLN}$	$> 1.1 \times \text{ULN}$
Specific gravity	—	—	$> 1.1 \times \text{ULN}$

LLN = lower limit of normal value provided by the laboratory; SI = *Le Système International d'Unités* (International System of Units); ULN = upper limit of normal value provided by the laboratory

Table B-2. Criteria for Potentially Clinically Significant Vital Signs

Parameter	Flag	Criteria ^a	
		Observed Value	Change From Baseline
Systolic Blood Pressure, mmHg - Postural Vital Signs (Supine and Standing)		Decrease in systolic blood pressure of 20 mmHg or more from supine to standing [*Change from supine SBP ≤ -20]	Decrease in SBP from supine to standing at observed time point is at least 10 mmHg greater than the decrease in SBP from supine to standing at baseline [Postbaseline change from supine SBP – baseline change from supine SBP ≤ -10]
Diastolic Blood Pressure, mmHg Postural Vital Signs (Supine and Standing)		Decrease in diastolic blood pressure of 10 mmHg or more from supine to standing [Change from supine DBP ≤ -10]	Decrease in DBP from supine to standing at observed time point is at least 10 mmHg greater than the decrease in DBP from supine to standing at baseline [Postbaseline change from supine DBP – baseline change from supine DBP ≤ -10]
Pulse Rate, bpm - Postural Vital Signs (Supine and Standing)		Increase in heart rate of 20 beats per minute or more from supine to standing [Change from supine pulse rate ≥ 20]	Increase in heart rate from supine to standing at observed time point is at least 10 beats per minute greater than the increase in heart rate from supine to standing at baseline [Postbaseline change from supine pulse rate – baseline change from supine pulse rate ≥ 10]

Parameter	Flag	Criteria^a	
		Observed Value	Change From Baseline
Systolic Blood Pressure, mm Hg (Supine)	High	Age 6-11 (inclusive): ≥ 140 Age 12-18 (inclusive): ≥ 155	Increase of ≥ 20
	Low	Age 6-11 (inclusive): ≤ 80 Age 12-18 (inclusive): ≤ 90	Decrease of ≥ 20
Diastolic Blood Pressure, mm Hg (Supine)	High	Age 6-11 (inclusive): ≥ 95 Age 12-18 (inclusive): ≥ 105	Increase of ≥ 15
	Low	Age 6-11 (inclusive): ≤ 40 Age 12-18 (inclusive): ≤ 45	Decrease of ≥ 15
Pulse Rate, bpm (Supine)	High	Age 6-11 (inclusive): ≥ 140 Age 12-18 (inclusive): ≥ 120	Increase of ≥ 15
	Low	Age 6-11 (inclusive): ≤ 50 Age 12-18 (inclusive): ≤ 40	Decrease of ≥ 15
Weight, kg	High	—	Increase of $\geq 5\%$
	Low	—	Decrease of $\geq 5\%$

bpm = beats per minute; DBP = diastolic blood pressure; SBP = systolic blood pressure

* Change from supine value = standing value – supine value.

a. A postbaseline value is considered potentially clinically significant if it meets both the observed-value and the change-from-baseline criteria.

Table B-3. Criteria for Potentially Clinically Significant Electrocardiograms

Parameter	Unit	Higher Limit
QRS interval	msec	QRS ≥ 115 msec (6-7 (inclusive) years) QRS ≥ 125 msec (8-15 (inclusive) years) QRS ≥ 150 msec (16-18 (inclusive) years)
PR interval	msec	PR > 225 msec (6-7 (inclusive) years) PR > 250 msec (8-18 (inclusive) years)
QTc(F)	msec	>480

QTc(F) = QT Corrected by Fridericia's formula

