2.2.4. Post-marketing Experience

In post-marketing experience, severe diarrhea AEs associated with dizziness, syncope, hypotension, and electrolyte abnormalities (hypokalemia and hyponatremia) requiring hospitalization or IV fluid administration have been reported in adult patients treated with linaclootide.

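### The urine specific gravity PCS limit (> 1.1 × ULN) cannot be reached, so its zero count is uninformative; on assumed reference ranges, sodium and chloride limits flag only extreme values

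*SAP*

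**What the plan says.** SAP Section 9.3 sets the rule: "Clinical laboratory test values will be considered potentially clinically significant (PCS) if they meet either the lower-limit or higher-limit PCS criteria" in Table B-1 of Appendix B. The PCS table counts participants with a non-PCS baseline and at least one PCS post-baseline value, out of those with a non-PCS baseline and any post-baseline value. A further display shows the adverse events of participants who had a PCS laboratory value.

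In Table B-1 the "Specific gravity" row has no lower limit and a higher limit of > 1.1 × ULN. The electrolyte rows include "Sodium mmol/L < 0.9 × LLN > 1.1 × ULN" and "Chloride mmol/L < 0.9 × LLN > 1.1 × ULN", and potassium, bicarbonate and magnesium carry the same multipliers. BUN is flagged above 1.2 × ULN and creatinine above 1.3 × ULN. The reference limits come from the laboratory and are not printed.

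Section 9.3 also plans descriptive statistics and low/normal/high shift tables from baseline to the end of the intervention period for the same analytes, specific gravity included.

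**The concern.** A percentage multiplier suits an analyte whose reference range is wide relative to its level. Specific gravity is the opposite case: its whole range is a few hundredths above 1.000, so 10% of the ULN is several times the width of the range. Sodium and chloride share the problem to a smaller degree.

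The subject matters in this study. The adverse events of special interest (AESIs) are volume depletion, electrolyte abnormalities and ECG abnormalities related to diarrhea (Protocol Section 8.3.1, SAP Section 9.2.6). Protocol Section 2.2.4 notes that "electrolyte abnormalities (hypokalemia and hyponatremia) requiring hospitalization or IV fluid administration have been reported in adult patients". Specific gravity measures urine concentration, so it bears on volume depletion, and sodium is the analyte behind hyponatremia. A printed zero in these rows would invite the reading that nothing happened. For specific gravity the rule can return nothing else.

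**Working it through.** The plan states no PCS rate, so there is no figure to reproduce. The multipliers are from Table B-1. All reference ranges below are assumptions.

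**1. Specific gravity.** Cut-off = 1.1 × ULN. If ULN > 1.000, then 1.1 × ULN > 1.100, whatever the laboratory.
- ULN 1.025: 1.1 × 1.025 = 1.1275
- ULN 1.030: 1.1 × 1.030 = 1.133
- ULN 1.040: 1.1 × 1.040 = 1.144

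For assumed ranges 1.001–1.025, 1.003–1.030, 1.003–1.035 and 1.001–1.040, the cut-off lies 2.7 to 4.3 reference-range widths above the ULN. With SD = (ULN − LLN)/(2 × 1.96), that is 12.4 to 18.7 SD above mid-range. The computed flag rate is zero even after a 2 SD upward shift. Because no baseline value can be PCS either, everyone with a baseline and a post-baseline value enters the denominator, and the row reads 0/n.

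**2. Other rows.** The same SD formula is used, with a normal distribution centered at mid-range and then shifted 1 or 2 SD toward the limit. For example, sodium 132–147 gives SD = 15/3.92 = 3.83 and a low limit of 0.9 × 132 = 118.8, which is (139.5 − 118.8)/3.83 = 5.4 SD below mid-range.

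| Analyte, assumed ranges | PCS limit | SD from mid-range | Flag rate, 1 SD shift | Flag rate, 2 SD shift |
|---|---|---|---|---|
| Sodium, 132–147, 135–145, 136–145 mmol/L | < 118.8 to < 122.4; > 159.5 to > 161.7 | 5.4–8.3 | below 0.001% | at most 0.03% |
| Chloride, 94–112, 96–109, 98–107 mmol/L | < 84.6 to < 88.2; > 117.7 to > 123.2 | 4.0–6.6 | at most 0.13% | at most 2.2% |
| Potassium (low), 3.3–5.5, 3.4–4.7, 3.5–5.1 mmol/L | < 2.97 to < 3.15 | 2.6–3.0 | 2.4–6.1% | 16–29% |
| Bicarbonate (low), 17–30, 20–28, 22–29 mmol/L | < 15.3 to < 19.8 | 2.5–3.2 | 1.4–7.0% | 12–32% |
| Magnesium (low), 0.6–1.0, 0.7–0.95 mmol/L | < 0.54 to < 0.63 | 2.6–3.1 | 2.0–6.1% | 15–29% |
| BUN, 1.4–8.6, 2.5–6.5 mmol/L | > 7.8 to > 10.3 | 2.9–3.2 | 1.3–2.9% | 11–19% |
| Creatinine, 27–62, 35–80 µmol/L | > 80.6 to > 104 | about 4.0 | about 0.1% | about 2% |

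**3. Expected counts in 120 participants** (the planned minimum, before the split by condition, dose and age):
- Sodium after a 2 SD shift: at most 120 × 0.00033 = 0.04
- Chloride after a 2 SD shift: at most 120 × 0.022 = 2.6
- Low potassium after only a 1 SD shift: 120 × 0.024 = 2.9 to 120 × 0.061 = 7.3

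**4. What the shift tables add.** In Protocol Tables 1–1 to 1–4 the only scheduled post-baseline laboratory sample is at the end-of-treatment visit. The shift table covers that sample at the unmultiplied limits. Protocol Section 8 allows unscheduled samples for safety reasons. The PCS count takes any post-baseline value, so it can include a sample drawn during a diarrhea episode that the shift table would miss.

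**The case against.** A reader might go further and infer that the plan's dehydration and electrolyte PCS rates as a whole will be near zero by construction. The documents do not support that. On the assumed ranges, the same 0.9/1.1 multipliers give potassium, bicarbonate and magnesium limits that a moderate shift would cross. Potassium also covers the hypokalemia half of the post-marketing concern. BUN and creatinine use other multipliers. Creatinine sits about as far out as the nearest chloride case, but nothing shows its limit to be unreachable. Postural blood pressure, postural pulse and weight have their own criteria in Table B-2.

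Nor is the PCS table the only safeguard. AESIs rest on investigator or sponsor judgement and have their own table and listing (SAP Section 9.2.6). Investigators must review laboratory reports and record clinically relevant changes as adverse events (Protocol Section 8.2.4). A zero specific gravity row cannot hide an AESI, and the shift tables show mild changes at the one scheduled post-baseline sample.

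It is also fair to say that how far beyond normal a sodium or chloride limit should sit is the sponsor's judgement. The distances above depend on assumed ranges, and for chloride the widest one allows a 2.2% flag rate after a 2 SD shift.

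All of this stands, and it confines the point to three rows. It does not rescue the specific gravity row, where no choice of laboratory range makes the rule workable.

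**Conclusion.** The specific gravity PCS criterion is inert as written. That conclusion needs only a ULN above 1.000 and the premise, from general physiology rather than the documents, that urine does not reach 1.10. Its zero row, and the absence of any specific-gravity-triggered entry in the adverse-event display, will carry no information.

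The sodium and chloride point is secondary and conditional. Under the assumed ranges and a normal model, sodium is flagged only at about 5.4 to 8.3 SD and chloride at about 4.0 to 6.6 SD. Zero or near-zero PCS counts in these rows should not be read as evidence of no effect. What is at stake is how three rows are interpreted; the capture of serious events and AESIs is not affected.

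**What to change.** **Specific gravity (correct).** Put the Table B-1 row on a usable scale in one of two ways.
- Apply the multiplier to the excess over water: flag above 1 + 1.1 × (ULN − 1). For an assumed ULN of 1.030 this is 1 + 1.1 × 0.030 = 1.033.
- Flag above the ULN. This repeats the shift table's high category for the scheduled sample, but adds unscheduled samples and brings flagged participants into the adverse-event display.

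**Sodium and chloride (consider).** The sponsor should consider limits scaled to the width of the reference range, or absolute limits. The documents give no laboratory ranges or alert values, so no replacement figure is offered here. If the present limits are kept, a table note should say that they detect only extreme values.

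The other rows need no change on this account. The cost is an edit to one SAP table, the matching change to the flagging program, and a few more values to list and review. No new data are collected and trial conduct is unaffected.
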